The SMILE Trial (Social and Monetary Incentives for Smoking Cessation at Large Employers) was designed to evaluate the impact of deposit contracts, individual bonuses, and team bonuses in isolation and in combination, relative to each other and a no-incentive control group.

The primary objective of this study is to compare the impact of multiple incentive designs versus usual care to increase smoking cessation among employees at participating worksites in the Bangkok metropolitan area of Thailand. The benchmark for effectiveness of the incentive

programs is usual care, offered in the form of brief group counseling and a text-messaging program for smoking cessation.

The secondary objectives of this study are to compare the net effects across study designs, taking into account program take-up, heterogeneous treatment effects, cost per Quitter, and social spillovers.

D. Study design

1. Study population

a. Eligibility criteria for worksites

Criteria for inclusion of companies in the study include:

- At least 200 workers
- At least 30 smokers employed at the worksite, according to estimates from worksite personnel
- Willingness to implement a randomly assigned intervention and to follow all aspects of the study protocol
- Being located in the Bangkok metropolitan area of Thailand

These criteria will be verified during conversations with a company officer prior to inclusion of the company in the study.

b. Eligibility criteria for participants

Inclusion criteria for study participants include:

- Being a full-time employee at a participating worksite
- Being an adult aged 18 years old or older
- Reporting having smoked at least 100 cigarettes in his or her lifetime
- Reporting smoking an average of at least 10 cigarettes per week
- Reporting wanting to quit smoking within the next 6 months

All of these criteria will be verified during a screening questionnaire, to be verified during an in-person baseline assessment.

Exclusion criteria:

- The individual expects to leave the company within the next year.
- The individual is unable to provide informed consent.
- The individual is currently pregnant.

- Pregnant women who smoke are not at higher risk from participating, but they belong under the supervision of a medical professional.

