1. Compile contact information for companies located in the targeted industrial areas.

2. During a phone conversation, give a brief introduction and request a brief in-person meeting to discuss the project.
3. Send a letter with the formal request to meet to the appropriate company official as an email attachment.
4. Attend an initial meeting at the worksite as an opportunity 1) to encourage the company officer to join the study and 2) to collect information about challenges and opportunities for recruitment at the company.
5. Hold a workshop to present additional information about the study to officials from worksites that agree to participate in the study.

b. Recruitment of participants

The recruitment of participants will occur in two batches of roughly 50 worksites each. The second batch will begin the intervention approximately three months following the start of the first batch. The staggered approach is designed to relieve some of the pressure on the field teams of having to be active in 100 worksites at once. It will also allow for minor changes in logistical planning to be adopted in Batch 2.

Prior to recruitment of participants, field personnel will make outreach visits to each worksite. During these visits, field personnel will set up a booth in a central location at the company, such as in the cafeteria during lunchtime, where they will provide information about the study and answer any questions.

The recruitment of participants at each company will proceed in three phases:

1. Identify all smokers who work at the company during a screening survey. Human resources and/or the health officer will assist with disseminating and collecting the screening surveys.
2. Conduct a baseline survey of all smokers who are eligible for the study, as determined in the screening survey.
3. Invite everyone who is eligible for the study to enroll as a participant in the study. We will send an invitation letter to each person, post flyers and posters around the worksite, and ask the health officer to assist with recruitment.

3. Interventions

The proposed study employs a cluster randomized controlled design with a 3-month intervention followed up 3, 6, and 12 months after enrollment. We will randomly assign participating worksites to treatment arms that vary on three cross-randomized components: 1) deposits or no deposits, 2) bonus size (none, small, large) and 3) teammate or individual.

a. Intervention components

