In total, there are 4 main intervention components:

C1. Usual care. All participants will receive usual care consisting of two elements: in-person group cessation counseling and cessation support via text messaging. The group counseling will consist of 90 minutes of counseling delivered at each worksite by a trained smoking cessation counselor. The text-messaging program, developed by the Thai Health Professional Alliance against Tobacco, will provide 1-3 messages per day for 28 days, which will include advice, support, and encouragement for quitting smoking. Similar programs have been found to be efficacious.⁴⁶ All materials will be delivered in Thai. Participants who do not own a mobile phone will be able to designate a family member to whom the messages can be sent. If the person cannot identify a phone number, the person will not receive the text messages.

C2. Deposits. Participants in deposit programs will be asked to provide refundable deposits contingent on smoking abstinence. These participants will receive a personal deposit box to take home and will make an initial deposit of at least 100 baht in the deposit box at the enrollment meeting. The deposit boxes, made out of metal, are designed to be tamper-proof. They have a coin slot but no other opening. Until the follow-up assessment at 3 months, participants will be able to make additional deposits in a lockbox that will be kept at the company. All deposits will be returned at the 3-month meeting only if the person has been determined to have quit smoking. At the 3-month follow-up assessment, study personnel will open each box using a can opener and will record the total balance.

At the enrollment meeting, participants will be required to give an additional 150-baht in collateral that depends solely on returning an intact deposit box at 3 months. The money will be placed in a sealed envelope with the participant's name on it to be stored at the project office in a locked cabinet. If the deposit box is tampered with or not returned at 3 months, then the money in the sealed envelope will be forfeited to the project.

C3. Teammate. Participants in team-based programs will be randomly assigned to another participant from the same worksite as a teammate. Team assignment will be stratified by work shift and native language in order to facilitate opportunities for communication. Pairings will be announced at the enrollment meeting at each worksite.

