C4. Cash bonus. Participants in small individual bonus programs will be eligible for a cash bonus of 600 baht for abstaining from smoking at 3 months. Participants in large individual bonus programs will be eligible for a bonus of 1,200 baht for abstinence at 3 months. This amount is roughly equivalent to one and two days' wages, respectively.

Participants in team bonus programs will be eligible for a team bonus of 1,200 baht each if both team members abstain from smoking at 3 months. The team bonus is designed to activate a sense of social commitment and peer pressure to quit. In teammate assignment strata with an odd number of participants, the "extra" participant did not receive a teammate and was, instead, eligible for a \$40 individual bonus.

b. Randomization groups

In total, there are 9 arms or randomization groups. The nine randomization groups are: 1) control group (usual care only), 2) 600-baht individual bonus, 3) 1,200-baht individual bonus, 4) team bonus, 5) deposits, 6) deposits plus teammate (no bonus), 7) deposits plus 600-baht individual bonus, 8) deposits plus 1,200-baht individual bonus, 9) deposits plus team bonus (Table 1).

Groups 2 and 3 are similar to incentives for smoking cessation used in many studies.⁴⁷ Incorporating both allows for a test of whether larger bonuses were more effective, as some researchers have hypothesized.⁴⁸ Group 5 is a “pure” deposit contract that replicates the intervention group in the CARES trial in the Philippines.²⁴ Group 6, involving a teammate and deposits but no other team-based incentives, will allow for identification of the independent effect of buddy-based peer support. Finally, group 9 combines a deposit contract with the same 1,200-baht team bonus in Arm 4, replicating the intervention used in White, Dow, and Rungruanghiranya.⁴⁹

Table 1. Crosswalk of randomization groups and intervention components

#	Randomization group	Intervention Component			
		Usual care	Deposits	600-baht bonus	1,200-baht bonus
1	Control	X			
2	600-baht individual bonus	X		X	
3	1,200-baht individual bonus	X			X
4	Team bonus	X			X X
5	Deposits	X	X		
6	Deposits plus teammate	X	X		X
7	Deposits plus 600-baht individual bonus	X	X	X	
8	Deposits plus 1,200-baht individual bonus	X	X		X
9	Deposits plus team bonus	X	X		X X

4. Study procedures

a. Consenting procedure

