We will use generalized linear mixed-effects models to estimate the intent-to-treat effect of each arm and each intervention component on program take-up and smoking abstinence. The generalized linear mixed-effects models will include a logit link for the binary outcome and a random intercept at the worksite level to adjust for the clustering of participants within a worksite. The primary outcome variable will be verified abstinence, treating reported NRT or e-cigarette use for cessation as abstinent as long as no cigarettes were used. We will report risk

differences from unadjusted and adjusted models. The adjusted models will include prespecified variables known to be related to the outcomes, including baseline demographic characteristics and smoking history. Demographic characteristics will include age (18-25, 26-35, 36-45, ≥ 45), gender, household income per capita, educational attainment (0-3, 4-6, 7-12, ≥ 13 years), marital status (married, not married), any children, and place of childhood (urban Thailand, rural Thailand, foreign country). Smoking characteristics will include average cigarettes per day, moderate-to-high nicotine dependence (Fagerström Test for Nicotine Dependence score ≥ 5), number of past quit attempts, number of years since initiating smoking, and quit intentions (want to quit within 3 months or not).

In sub-analyses, we will pool Groups 2-9 to compare the average effect of receiving usual care plus any incentive program, compared with usual care (Group 1), using similar adjusted and unadjusted mixed-effects models to those described above. We will also investigate interaction effects between intervention components, using the same adjusted mixed-effects models as above. We will also investigate whether those in a bonus group or deposit group are more likely to relapse following the end of the incentive period.

We will perform four sensitivity analyses to assess the robustness of the estimated intervention effects. First, we will conduct the analysis on a per-protocol basis, that is, among those who had accepted their assigned intervention. Second, we will use complete outcome data without assuming that missing cases had smoked. Third, we will exclude from the analysis the outcome data from participants who reported currently using NRT or e-cigarettes. Fourth, we will perform multiple imputation using chained equations to impute missing outcome data at each end point.

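### Does leaving the component coding unwritten let the team bonus contaminate the estimate of buddy support?

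*Combined protocol and SAP*

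**What the plan says.** D.8.b plans mixed-effects logistic models to "estimate the intent-to-treat effect of each arm and each intervention component on program take-up and smoking abstinence", reported as risk differences. It adds an investigation of interactions between components without naming them. It gives no model equation or list of indicator variables.

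The components are described in several places:

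- Study objectives (C) sets out to "evaluate the impact of deposit contracts, individual bonuses, and team bonuses in isolation and in combination".
- Interventions (D.3) speaks of "three cross-randomized components: 1) deposits or no deposits, 2) bonus size (none, small, large) and 3) teammate or individual".
- Intervention components (D.3.a) says "In total, there are 4 main intervention components": C1 usual care, C2 deposits, C3 teammate, C4 cash bonus. Under C3, "Participants in team-based programs will be randomly assigned to another participant from the same worksite as a teammate". Under C4 there is a small individual bonus, a large individual bonus and a team bonus, whose recipients are "eligible for a team bonus of 1,200 baht each if both team members abstain from smoking at 3 months". C4 adds: "The team bonus is designed to activate a sense of social commitment and peer pressure to quit".
- Randomization groups (D.3.b) says of Group 6 that it is an arm "involving a teammate and deposits but no other team-based incentives, will allow for identification of the independent effect of buddy-based peer support".

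The background section on social support says that this question will be addressed by comparing depositors who have a partner with depositors who do not.

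**The concern.** The objectives name the team bonus and no separate teammate. D.3 and Table 1 name the teammate and treat the team bonus as teammate plus 1,200 baht. These descriptions can lead to different regression models, and D.8.b does not choose between them.

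The choice matters because of the arms that exist. A teammate without a bonus occurs only in Group 6. A teammate with 1,200 baht occurs in Groups 4 and 9, and there the money is always the joint bonus. A main-effects model on the Table 1 columns has one teammate coefficient to describe both situations. If buddy support does nothing and the joint bonus works, that coefficient would be positive and could be read as evidence for buddy support. At stake are the component and mechanism results, not the effect of each arm against usual care.

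**Working it through.** **Inputs.** Nine arms in equal proportion (Randomization, D.5); arm composition from Table 1 and D.3.b. The documents give no size for the buddy or team-bonus effects, so any effect sizes below are assumptions. The plan states no figure for component effects, so there is none to reproduce.

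**Step 1: main effects on the Table 1 columns.** With X holding an intercept and indicators for deposits, 600 baht, 1,200 baht and teammate, the weights on the nine arm means are (X'X)⁻¹X'. For the teammate coefficient:

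| Arm | 1 | 2 | 3 | 4 | 5 | 6 | 7 | 8 | 9 |
|---|---|---|---|---|---|---|---|---|---|
| Weight | −0.143 | 0.048 | −0.262 | 0.357 | −0.238 | 0.381 | −0.048 | −0.357 | 0.262 |

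The weight on the team-bonus arms is 0.357 + 0.262 = 0.619, and on Group 6 it is 0.381. So

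teammate coefficient = 0.381 × buddy + 0.619 × (team bonus minus individual 1,200 baht).

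Write the team-bonus extra as the team-bonus effect beyond buddy support plus 1,200 baht. The coefficient is then buddy + 0.619 × extra, and the 1,200-baht coefficient absorbs 0.381 × extra. Giving any one arm a twelfth worksite (eight arms of 11, one of 12) moves the 0.619 only within 0.607 to 0.624.

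For an assumed extra of −3 to +5 points:

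- teammate is displaced by 0.619 × (−3) = −1.9 to 0.619 × 5 = +3.1 points;
- 1,200 baht is displaced by 0.381 × (−3) = −1.1 to 0.381 × 5 = +1.9 points.

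If the extra is zero, nothing is displaced.

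**Step 2: C2, C3 and C4 coded as D.3.a describes them.** The indicators are deposits, teammate, and a bonus with four levels (none, 600 individual, 1,200 individual, team). The model has full rank, with six parameters on nine arms. The teammate weights become:

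| Arm | 1 | 2 | 3 | 4 | 5 | 6 | 7 | 8 | 9 |
|---|---|---|---|---|---|---|---|---|---|
| Weight | −0.375 | 0.125 | 0.125 | 0.125 | −0.625 | 1 | −0.125 | −0.125 | −0.125 |

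The loading on Groups 4 and 9 is 0.125 − 0.125 = 0. The individual 1,200-baht term also has zero loading.

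**Step 3: the objectives sentence read as a model.** Deposits, two individual bonuses and the team bonus, with no teammate term, would leave Group 6 coded as deposits only. Its buddy effect would leak into deposits (+0.154) and each bonus term (−0.308). But this reading ignores C3, and the objectives sentence does not claim to list components.

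**Step 4: the source of the mixing.** Crossing the three factors gives 2 × 3 × 2 = 12 cells, of which nine are run, so the empty cells look responsible. They are not. With all 12 cells filled and the extra placed where teammate meets 1,200 baht, a main-effects fit still loads 0.33 on teammate and 0.50 on 1,200 baht. The omitted teammate-by-1,200 term causes the mixing; the empty cells only alter the weights.

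**Step 5: the price of separating the effects.** Variance factors are sums of squared weights, in units of one arm-mean variance:

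| Estimate | Main effects (Step 1) | Separated (Step 2) | SE ratio |
|---|---|---|---|
| Buddy, component model | 0.619 | 1.625 | √(1.625/0.619) = 1.62 |
| Buddy, Group 6 vs 5 | 0.619 | 2.000 | √(2/0.619) = 1.80 |
| 1,200 baht | 0.619 | 1.000 | √(1/0.619) = 1.27 |

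**The case for a change.** The strongest case for a change is that D.8.b promises component effects and leaves open models with different answers. Planning interactions in general terms does not settle it: adding only deposit × teammate still leaves a loading of 0.50 among depositors. Even with the teammate-by-1,200 term fitted, a teammate risk difference averaged over all nine arms would return buddy plus 4/9 = 0.44 of the extra, because four of the nine arms carry 1,200 baht. On the logit scale, with assumed control abstinence of 6% and odds ratios of 1.3, 1.4 and 1.8 for deposits, 600 and 1,200 baht, a true buddy odds ratio of 1.0 with a team-bonus odds ratio of 2.0 gives a main-effects teammate odds ratio of 1.67. Writing out the coding would cost one paragraph.

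The arithmetic in that case stands, and an explicit coding would have been tidier. What does not stand is the step from an unwritten model to a faulty one. The harm requires three things together: the team bonus collapsed into 1,200 baht, the relevant interaction left out or averaged over, and a pooled coefficient presented as buddy support. The plan states none of these, and the protocol's account of Group 6 points away from the last. A pooled teammate main effect is also a legitimate factorial average and the more precise estimate, provided it is described as covering both buddy support and the team bonus.

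**Conclusion.** The concern does not call for a change. D.8.b leaves the component coding unstated, but the protocol supplies what an analyst needs: C3 and C4 keep the teammate apart from the three kinds of bonus, the background and D.3.b tie buddy support to depositors and Group 6, and the planned arm effects yield Group 6 versus Group 5 with no contribution from the team-bonus arms.

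The mixture of 0.38 and 0.62 belongs to one possible way of filling the gap. It rests on equal arms, a linear risk-difference scale and main effects only, and it misleads only if the team-bonus extra is not zero, for which the documents give no value. Choosing between the separated and pooled estimates is a fair trade-off, since separation raises the buddy standard error by a factor of 1.62 to 1.80.

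One limit belongs to the design under any coding: no arm pairs a teammate with an individual bonus, so the both-must-abstain rule cannot be distinguished from synergy between having a buddy and being paid. The comparisons of each incentive arm with usual care do not depend on any of this.

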After providing a urine sample, each participant will complete a short survey administered by study personnel on a portable tablet. A separate module will be administered for self-reported quitters and self-reported continuing smokers, as determined at the start of the questionnaire. All respondents will be asked questions related to smoking behavior and quit attempts since the prior meeting. Participants will also be asked additional questions about their behavior during the intervention period and their perceptions related to the intervention.

At the end of the follow-up visit, each participant will receive an inconvenience gift worth 150 baht. Participants may choose to be paid in cash or in kind.

A field team member will contact by phone the participants who do not attend the follow-up visit to ascertain their self-reported smoking status. The reason for non-attendance will be recorded. If a participant reports having abstained, a field worker will schedule a time within the next 48 hours to provide a urine sample for biochemical verification. Those who provide the urine sample will receive the inconvenience gift worth 150 baht.

5. Randomization

After baseline surveys are completed, worksites will be randomly assigned in equal proportion to one of the nine randomization groups. The cluster randomized design mitigated concerns of within-worksite contamination and is expected to be viewed by employers as more acceptable than person-level randomization. We will follow a covariate-adaptive procedure, in which we will minimize the *p*-value from a joint *F*-test as a balance criterion implemented over 1,000 iterations.⁵⁰ In Monte Carlo simulations, minimization has been found to facilitate covariate balance.⁵¹ The randomization procedure will include the following worksite-level covariates, which we will also include in the adjusted regression analyses: province, mean age, mean proportion born in Thailand, mean cigarettes per week, mean proportion who want to quit smoking within 6 months, number of employees, and estimated smoking prevalence based on baseline data.

A study investigator will implement the random allocation sequences using computer-generated random numbers, concealing the sequence from field staff, company employees, and participants until after the baseline survey has been completed. Participants will be informed of their assignment in an enrollment invitation letter sent following the baseline survey.

6. Outcomes

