The proposed sample size is 6,000 participants drawn from 100 worksites. This sample size is larger than previous studies that use incentives or commitment contracts for smoking cessation. For example, the sample size is more than double all but one study included in a recent systematic review of competitions and monetary incentives for smoking cessation.¹³

A preliminary survey of 37 firms who attended a workshop in September 2011 indicated that the median firm has 800 employees, roughly 20% of whom smoke. Of the 37 firms, 35 (95%) expressed an interest in joining the project, implying that the target of recruiting 100 worksites is feasible. Based on the survey data and the pilot study, we expect trial take-up to vary from 10% of smokers in the control arm to 70% in the larger individual bonus arm, and quit rates conditional on take-up to vary from 20% in the control arm to 45% in the deposit contract with a team bonus.

Using Optimal Design Software,⁵³ we computed the minimum detectable effects for a binary abstinence measure as a function of a cluster-randomized binary treatment using a multi-level equation (person at level 1, worksite at level 2) with a random effect for each worksite. We estimated that we will be able to detect absolute differences of at least 7.5 percentage points in abstinence rates for pairwise comparisons between any of the incentive-based arms versus the usual-care control group. This calculation assumed an abstinence rate of 6.0% in the control group (10% conditional on 60% program take-up), 60 participants per worksite, Type-I error $\alpha = 0.05$, and 80% power ($\beta = 0.20$).

Our reported detectable effect sizes are conservative in that they do not adjust for stratification variables used for firm-level randomization (i.e., firm size, industry type, and smoking prevalence) or baseline control variables, both of which will reduce the variance of parameter estimates and, thus, the detectable effect size.

b. Planned statistical analyses

We will conduct descriptive analyses as components of standard data analyses. To evaluate balance across groups achieved by randomization, baseline values of all control variables will be compared across the 9 arms using *t*-tests.

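### Pooling the eight incentive arms in one indicator would count designed arm differences as worksite noise and cost the any-incentive contrast some precision

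*Combined protocol and SAP*

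**What the plan says.** All references are to the combined protocol and SAP.

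- Section D.8.b, main analysis: logit mixed models will "estimate the intent-to-treat effect of each arm and each intervention component on program take-up and smoking abstinence". They include "a random intercept at the worksite level to adjust for the clustering of participants within a worksite", and results are reported as risk "differences from unadjusted and adjusted models".
- Section D.8.b, sub-analyses: "we will pool Groups 2-9 to compare the average effect of receiving usual care plus any incentive program, compared with usual care (Group 1"). The plan describes the method for this comparison only as "using similar adjusted and unadjusted mixed-effects models to those described above". No arm terms, arm-level variance or contrast are mentioned for it.
- Section D.5: "worksites will be randomly assigned in equal proportion to one of the nine randomization groups".
- Section D.8.a: "The proposed sample size is 6,000 participants drawn from 100 worksites". The same section expects the arms to behave very differently: "we expect trial take-up to vary from 10% of smokers in the control arm to 70% in the larger individual bonus arm", with quit rates among those who take up running from 20% to 45%.

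**The concern.** The target is an average over eight programs fixed by design, so differences between them are not sampling error. Arm is a worksite-level factor. Once the eight arms share one indicator, the only term left to take up their differences is the worksite random intercept.

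The model applies that one variance to every worksite, including the roughly 11 control worksites, and these dominate precision. In 1/11 + 1/89 = 0.0909 + 0.0112 = 0.1021, the control group supplies 0.0909/0.1021 = 89%.

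This comparison gives a single answer on whether incentives beat usual care, and it uses every worksite. With one indicator, it loses power as the designs differ more, for example when only some of them work.

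**Working it through.** **Inputs from the plan.** Nine arms in equal proportion and 100 worksites, so about 11 control and 89 incentive worksites; 60 participants per worksite; control abstinence 6.0%; detectable difference 7.5 points; alpha 0.05 (taken as two-sided) and 80% power.

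**Assumed, because the plan does not state them.** The ICC and the abstinence rate in each arm.

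**Step 1: the ICC implied by the plan's own figure.** Detecting 6.0% versus 13.5% under individual randomization needs 245 per arm. The plan has 11 × 60 = 660 per arm, so the design effect is 660/245 = 2.69 and the ICC is (2.69 − 1)/59 = 0.029. A t-based version with about 20 degrees of freedom gives 0.025. The 7.5 points cannot be checked independently without the ICC, but a value near 0.03 is consistent with it.

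**Step 2: closed form for worksite means.** SE ratio (pooled over nine-arm) = √(1 + 0.89 × V/s²). Here 0.89 is the share of worksites in incentive arms, V is the variance of the eight arm rates, and s² is the variance of a worksite mean: the nine-arm average of p(1 − p), times (1 + 59 × 0.03)/60. With four arms at 6% and four at 13.5%, V = 0.0375² = 0.00141 and s² = 0.0832 × 2.77/60 = 0.00384. The ratio is √(1 + 0.89 × 0.00141/0.00384) = 1.15.

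**Step 3: simulation of the planned model.** Logit random-intercept model, maximum likelihood, 100 worksites of 60, 300 runs per scenario. The SE of the risk difference from one pooled indicator was compared with that of the equal-weight mean of eight arm effects from the nine-arm model. Control is 6% throughout. The last two columns are at ICC 0.03.

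| Incentive arms | Closed form, ICC 0.03 | Simulated SE ratio, ICC 0.01 / 0.03 / 0.05 | Pooled SE over its actual sampling SD | Coverage, pooled / nine-arm |
|---|---|---|---|---|
| All 6% | 1.00 | 1.04 / 1.04 / 1.04 | 0.0140/0.0145 = 0.97 | 94.3% / 92.3% |
| Even, 6-13.5% | 1.07 | 1.13 / 1.10 / 1.09 | 0.0158/0.0155 = 1.02 | 95.3% / 93.3% |
| Four at 6%, four at 13.5% | 1.15 | 1.27 / 1.20 / 1.16 | 0.0171/0.0157 = 1.09 | 97.0% / 93.3% |
| Even, 6-20% | 1.18 | 1.26 / 1.20 / 1.16 | 0.0178/0.0166 = 1.07 | 96.7% / 93.3% |
| Even, 6-25% | 1.28 | 1.37 / 1.26 / 1.21 | 0.0196/0.0173 = 1.13 | 97.3% / 93.0% |

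The mechanism is visible in the estimated worksite SD on the logit scale. For arms at 6-20% it was 0.70 with one indicator and 0.53 with nine arms, against a true 0.57.

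The 1.04 with equal arms is not inflation. It shows that the nine-arm maximum-likelihood SE is slightly too small, so about 4 points of every simulated ratio come from that source.

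**Step 4: the same comparison with that bias removed.** Both analyses were run on worksite proportions with df-corrected variances.
- Even spread 6-13.5%: pooled SE 8% larger, power 48% versus 56%.
- Four arms at 6%, four at 13.5%: pooled SE 17% larger, power 38% versus 55%.

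Coverage was at least 95% for both analyses. The mean effect is 9.75 − 6 = 3.75 points in each case.

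**Step 5: take-up.** With control 10%, arms assumed evenly spread over 10-70% and worksite SD 0.55, the pooled SE was 78% larger and the pooled estimate's actual sampling SD was 46% larger (3.3 versus 2.3 points). With arms at 20-70% and SD 0.8, the pooled SE was 30% larger and pooled coverage fell to 92%. Power was 100% either way.

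**The case against.** - **The text does not literally say one indicator.** An average effect could be obtained by averaging arm effects from the nine-arm model. That is true, but pooling groups in similar models is more naturally read as merging them, and a sponsor who intends a contrast needs only to say so.
- **The pooled interval is not much too wide for its own estimator.** Against the actual sampling SD, the excess for abstinence is 2-9% for moderate spreads at ICC 0.03. Coverage stays at or above 95% whenever arms differ. This stands: for abstinence the error is conservative.
- **The nine-arm contrast is not free.** With uncorrected maximum likelihood it covered about 93%. In a separate run of 400 with equal arms it rejected 7.3%, against 5.8% for the pooled model. Part of the apparent power gain from switching is therefore bought with an SE that is too small. This stands too, and is why the fix must carry a correction. Step 4 shows that the gain survives once both analyses are corrected.
- **The stakes are limited.** This is a sub-analysis. The arm-by-arm estimates do not depend on it, and at ICC 0.03 the pooled abstinence estimate was off by at most 0.35 points over the spreads tabulated.

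A reader might infer that the interval is up to 25% too wide. The documents support neither that figure nor any upper bound. Reaching it needs an assumed spread, such as arms at 6-25% with ICC 0.03, and it counts the nine-arm underestimation as inflation. The ranges in section D.8.a do not settle the spread, because they concern take-up and quitting given take-up and are not stated to be 12-month abstinence.

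**Conclusion.** The point holds as a loss of precision in one sub-analysis. For 12-month abstinence, the any-incentive SE is roughly 5-20% larger than needed when arm rates lie within 6-13.5% up to 6-20%. It is larger for wider spreads, and not inflated if the eight arms are equal. The loss matters most if only some designs work: power was 38% rather than 55% when four arms had no effect and four had the plan's own detectable difference. For take-up the loss of precision is greater, though power is not at risk, and under one assumed spread the pooled interval also under-covered.

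These sizes rest on assumed arm rates and an ICC near 0.03, equal worksite sizes, normal worksite effects with a common variance, and no covariates.

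The documents do not support a reading in which the pooled abstinence result would be falsely positive, or in which the main comparisons of each arm with usual care are affected.

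**What to change.** In section D.8.b, state that the pooled effect is the equal-weight mean of the eight incentive arms' marginal risks minus the Group 1 risk. Estimate it as a contrast from the nine-arm mixed model already planned, for both abstinence and take-up, unadjusted and adjusted. State a small-sample correction as well, for example a REML-type or df-corrected variance with a t reference, because only about 11 worksites are controls and the maximum-likelihood SE is otherwise slightly too small. This also fixes the weighting of the arms in advance.

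The cost is a sentence or two in the plan, slightly more analysis work, and the need to choose and carry out the correction. No new data are needed.
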